
5.1 Follow-up for Ineligible Patients

The follow-up requirement for ineligible patients who have received no protocol chemotherapy and have not had excision procedure only includes submission of the Baseline Report.

Ineligible participants who have received at least one dose of protocol chemotherapy and/or have had TEMS/TAMIS procedure should be followed as per protocol requirements to allow for treatment and adverse event assessment.

6.0 ENTRY/ENROLLMENT PROCEDURES

6.1 Entry Procedures

All enrollments will be done through the CCTG web-based, password-operated Electronic Data Capture (EDC) system. Complete details regarding obtaining a password, accessing the system and enrolling patients will be provided at the time of study activation and will also be included in the "EDC Data Management Guidebook", posted on the CO.28 trial specific web-site. If sites experience difficulties accessing the system and/or enrolling patients please contact the help desk (link in EDC) or the CO.28 Study Coordinator.

All eligible patients enrolled on the study by the participating treatment centre will be assigned a serial number which must be used on all documentation and correspondence with CCTG.

The following information will be required:

- trial code (CCTG CO.28)
- patient's initials (may be coded)
- informed consent version date, date signed by patient, name of person conducting consent discussion and date signed
- tissue banking/optional consent version date
- confirmation of the requirements listed in Section 5.0, including dates of essential tests and actual laboratory values
- BSA, height and weight

6.2 BSA Calculation

In calculating surface areas, actual heights and weights should be used, that is, there will be no downward adjustment to "ideal" weight. This principle applies to individuals whose calculated surface area is 2.2 m^2 or less. In those rare cases where a patient's surface area is greater than 2.2, the actual surface area or 2.2 may be used. CCTG BSA calculations are based on the Mosteller formula.

6.3 Enrollment

Enrollment will be provided electronically.

Note: The validity of results of the trial depends on the authenticity of and the follow-up of all patients entered into the trial. Under no circumstances, therefore, may an allocated patient's data be withdrawn prior to final analysis, unless the participant withdraws from the trial and requests that data collection/submission cease from the point in time of withdrawal.

All eligible patients admitted to the trial will be followed by the coordinating centre. It is the responsibility of the physician in charge to satisfy himself or herself that the patient is indeed eligible before requesting enrollment.

All enrolled patients are to be followed until death or until sites are informed by CCTG that further follow-up is no longer required. The follow-up requirements for ineligible patients are outlined in Section 5.1.

7.0 TREATMENT PLAN

Although the Canadian Cancer Trials Group acts as the coordinating agency for the trial, the responsibility for treatment of patients rests with the individual investigator.

In accordance with CCTG policy, protocol treatment is to begin within 5 working days of patient enrollment.

7.1 Chemotherapy Treatment Plan

FOLFOX or CAPOX is selected based on investigator discretion.

7.1.1 Drug Administration

7.1.1.1 **FOLFOX (5-fluorouracil + leucovorin + oxaliplatin)**

Agent(s)	Dose	Route	Duration	Schedule
Oxaliplatin	85 mg/m ²	IV over 2 hours	Day 1	Repeat every 14 days for a total of 6 cycles
Leucovorin	400 mg/m ² bolus	IV over 2 hours	Day 1	Repeat every 14 days for a total of 6 cycles
5FU	400 m/m ² bolus over 5 - 15 minutes then 2400 mg/m ² continual infusion over 46 - 48h total dose	IV	Days 1 to 2	Repeat every 14 days for a total of 6 cycles

1. Oxaliplatin could be administered first, prior to leucovorin; or concurrently with leucovorin administered via separate infusion containers.
2. If necessary to accommodate holidays, patient schedule or other justified circumstance, the schedule may be delayed up to 7 days.
3. Patients who cannot tolerate six cycles of FOLFOX or those that require dose modification below dose level -2 (see Section 7.1.3.1) may receive preoperative 5FU chemoradiotherapy based on investigator decision. If chemoradiotherapy is given, it should be given according to local institutional guidelines for FOLFOX administration. There are no restrictions on dose modifications for the 6th cycle of neoadjuvant FOLFOX.
4. Alternate folinic acids (i.e. levo-leucovorin) may be substituted for Leucovorin if not available. Note: Levo-leucovorin is twice as potent as leucovorin; dosages should be adjusted accordingly. Dosages are at the discretion of the treating physician. Dose modifications of leucovorin up to and including omission of leucovorin or its analogues imposed by drug shortages will not constitute protocol violations.
5. The dose modification schema for FOLFOX (see Section 7.1.3.1) is suggested. Oncologists may use clinical judgment in making dose modifications that deviate from the suggested schema. These will not constitute protocol violations.

7.1.1.2 ***CAPOX (capecitabine + oxaliplatin)***

Agent(s)	Dose	Route	Duration	Schedule
Capecitabine	1000 mg/m ² BID	PO	14 days starting on Day 1	Repeat every 21 days for a total of 4 cycles
Oxaliplatin	130 mg/m ²	IV over 2 hours	Day 1	Repeat every 21 days for a total of 4 cycles

1. Patients must be counseled about the importance of compliance with capecitabine. Compliance, with mention of missed doses, must be documented in the patient's medical record by site study personnel.
2. Missed doses must be documented on the appropriate CRF and by patients on their provided diary.
3. Patients should take their doses of capecitabine orally daily, one dose in the morning and one dose in the evening, approximately 12 hours apart. Patients should swallow capecitabine tablet(s) whole with a full glass of water, about 8 ounces, within 30 minutes after a meal. Patients should not try to make up a missed or vomited dose, never double up on a dose and tell their doctor if they miss a dose. Patients must return any remaining capecitabine tablets at their next study visit.

7.1.2 Premedication

All patients should be pre-medicated as per institutional guidelines.

7.1.3 Dose Adjustments

Doses will be reduced for hematologic and other adverse events. Dose adjustments are to be made according to the system showing the greatest degree of toxicity. Adverse events will be graded using the NCI Common Terminology Criteria for Adverse Events (CTCAE) (see Appendix III).

The major toxic effects which limit dose are hematologic. The guidelines which follow outline dose adjustments for several of these toxic effects. If a patient experiences several adverse events and there are conflicting recommendations, please use the recommended dose adjustment that reduces the dose to the lowest level.

7.1.3.1 *FOLFOX*

The precise dose modification schema used and the symmetry of dose modification (e.g., reduce both 5FU and oxaliplatin symmetrically, or one preferentially) may be left to the discretion of the treating oncologist. **The modification schema in Table Dose levels of FOLFOX is a guideline.** Leucovorin dose may be decreased in concert with bolus 5-FU dose. If 5-FU is not administered, leucovorin should not be administered.

1. **Dose reduction:** If a patient requires a dose reduction below level -2 during cycles 1-5 preoperative therapy, consider discontinuing FOLFOX and referring the patient for TME. This does not apply for cycle 6.
2. **Dose delay:** If FOLFOX is held due to toxicity for more than 30 days from planned next cycle date consider discontinuing FOLFOX and referring the patient for TME. This does not apply for cycle 6.

Dose levels of FOLFOX

Dose Level*	5-FU infusion	5-FU bolus	Oxaliplatin
0	1200 mg/m ² /day x 2 days (2400 mg/m ² over 46-48 hours)	400 mg/m ²	85 mg/m ²
-1	960 mg/m ² /day x 2 days (1920 mg/m ² over 46-48 hours)	320 mg/m ²	65 mg/m ²
-2	800 mg/m ² /day x 2 days (1600 mg/m ² over 46-48 hours)	270 mg/m ²	50 mg/m ²
-3**	680 mg/m ² /day x 2 days (1360 mg/m ² over 46-48 hours)	230 mg/m ²	40 mg/m ²

* Dose level 0 refers to the starting dose.
 ** If dose reduction below level -2 is required during cycles 1-5 of neoadjuvant therapy for a Group 1 patient, FOLFOX should be discontinued and the patient referred for standard surgical therapy. Dose reduction to level -3 is only permitted during cycle 6.

Suggested FOLFOX Dose Modifications Based on Interval Adverse Events

The following describe actions in the Dosage Change column:

- Omit = Treatment is not given for this cycle
- Hold = Treatment can be made up as part of this cycle
- Discontinue = Treatment is totally stopped

SYSTEM/ORGAN/CLASS (SOC)	ADVERSE EVENT	AGENT	DOSAGE CHANGE
BASED ON INTERVAL ADVERSE EVENT (Occurring before Day 1 of Cycle)			
Other Non-hematologic	Grade \geq 2 (excluding alopecia)	5-FU Oxaliplatin	Hold treatment until \leq grade 1 then resume at next lower dose level.

Dose Modifications Based on Retreatment (days 2-14 during previous cycle)

SYSTEM/ORGAN /CLASS (SOC)	ADVERSE EVENT	AGENT	DOSAGE CHANGE
AT TIME OF RETREATMENT (occurring at Days 2-14 during cycle)			
Gastrointestinal disorders	Nausea grade 2	Oxaliplatin	Intensify antiemetic therapy and proceed with FOLFOX at current dose level. Maximal antiemetic therapy includes a 5HT inhibitor (i.e. granisteron, ondansetron, palonestron) as well as compazine, lorazepam, aprepitant, and decadron
	Nausea grade 3		If resolved to < grade 2 on day of treatment, may proceed with intensification of antiemetic therapy and current dose level of FOLFOX. If not resolved to < grade 2 on day of therapy, intensify antiemetic regimen and proceed with FOLFOX when resolved to < grade 2. May decrease oxaliplatin one dose level if not responsive to maximal antiemetic support.
	Nausea grade 4		If resolved to < grade 2 on day of treatment, may proceed with intensification of antiemetic therapy and current dose level of FOLFOX. If not resolved to < grade 2 on day of therapy, intensify antiemetic regimen and proceed with FOLFOX when resolved to < grade 2. Decrease oxaliplatin one dose level if not responsive to maximal antiemetic support.
	Vomiting grade 2	5-FU Oxaliplatin	Intensify antiemetic therapy and proceed with FOLFOX at current dose level. Maximal antiemetic therapy includes a 5HT inhibitor (i.e. granisteron, ondansetron, palonestron) as well as compazine, lorazepam, aprepitant, and decadron.
	Vomiting grade 3		If resolved to < grade 2 on day of treatment, may proceed with intensification of antiemetic therapy and current dose level of FOLFOX. If not resolved to < grade 2 on day of therapy, intensify antiemetic regimen and proceed with FOLFOX when resolved to < grade 2. May decrease oxaliplatin one dose level if not responsive to maximal antiemetic support.
	Vomiting grade 4		If resolved to < grade 2 on day of treatment, may proceed with intensification of antiemetic therapy and current dose level of FOLFOX. If not resolved to < grade 2 on day of therapy, intensify antiemetic regimen and proceed with FOLFOX when resolved to < grade 2. Decrease oxaliplatin one dose level if not responsive to maximal antiemetic support.
	Diarrhea grade 2		If resolved to < grade 2, intensify antidiarrheal therapy and proceed with FOLFOX at current dose level. If not resolved to < grade 2, HOLD FOLFOX, intensify antidiarrheal therapy and proceed with FOLFOX when resolved to < grade 2.
	Diarrhea grade 3		If resolved to < grade 2, intensify antidiarrheal therapy and proceed with FOLFOX, decreasing 5FU and oxaliplatin one dose level. If not resolved to < grade 2, HOLD FOLFOX, intensify antidiarrheal therapy and proceed with FOLFOX decreasing 5FU one dose level when resolved to < grade 2
	Diarrhea grade 4		If resolved to < grade 2, intensify antidiarrheal therapy and proceed with FOLFOX, decreasing 5FU and oxaliplatin one dose level. If not resolved to < grade 2, HOLD FOLFOX, intensify antidiarrheal therapy and proceed with FOLFOX decreasing 5FU and oxaliplatin one dose level when resolved to < grade 2

table continues on next page

SYSTEM/ORGAN /CLASS (SOC)	ADVERSE EVENT	AGENT	DOSAGE CHANGE
AT TIME OF RETREATMENT (occurring at Days 2-14 during cycle) - CONTINUED			
Gastrointestinal disorders continued	Oral mucositis, Esophagitis, gastritis, pharyngeal mucositis, small intestinal mucositis, colitis, rectal and/or anal mucositis grade 3	5-FU Oxaliplatin	Hold FOLFOX until mucositis improves to < grade 2 then resume with one dose level reduction of 5-FU and the previous dose level of oxaliplatin
	Oral mucositis, Esophagitis, gastritis, pharyngeal mucositis, small intestinal mucositis, colitis, rectal and/or anal mucositis grade 4		Hold FOLFOX until mucositis improves to < grade 2 then resume with two dose level reduction of 5-FU and the previous dose level of oxaliplatin
AT TIME OF RETREATMENT (occurring at Days 11-14 during cycle)			
Blood and lymphatic system disorders	Neutropenia ANC 1.0 to 1.199 x 10 ⁹ /L	5-FU Oxaliplatin	Hold FOLFOX until ANC ≥ 1200 then resume at previous dose levels.
	Neutropenia ANC < 1.0 x 10 ⁹ /L		Hold FOLFOX until ANC ≥ 1200 then resume with one dose level reduction of both 5-FU and oxaliplatin for all subsequent cycles or at same dose level with GCSF at standard doses.
	Febrile neutropenia ANC < 1.0 x 10 ⁹ /L and temp ≥ 38.5° C		Hold FOLFOX until fever has resolved and ANC ≥ 1200 then resume with one dose level reduction of both 5-FU and oxaliplatin for all subsequent cycles or at same dose level with GCSF at standard doses.
	Thrombocytopenia Platelets 50 to 74.999 x 10 ⁹ /L		Hold FOLFOX until platelets ≥ 75,000 then resume at previous dose levels. except bolus 5-FU which is reduced by one dose level.
	Thrombocytopenia Platelets < 50 x 10 ⁹ /L		Hold FOLFOX until platelets ≥ 75,000 then resume FOLFOX with one dose level reduction of both 5-FU and oxaliplatin for all subsequent cycles
ENT	Pharyngolaryngeal dysesthesia	Oxaliplatin	Increase the duration of oxaliplatin infusion to six hours for all subsequent cycles. See section 8.4
Pulmonary disorders	Cough, dyspnea, hypoxia, pneumonitis or pulmonary infiltrates, grade ≥ 3.	5-FU Oxaliplatin	Hold oxaliplatin until interstitial lung disease is ruled out. Continue 5-FU/leucovorin. Discontinue study if interstitial lung disease is confirmed.
Thrombotic microangiopathy	Hemolytic uremic syndrome (HUS) ≥ grade 3	5-FU Oxaliplatin	Discontinue oxaliplatin. Continue 5-FU/leucovorin.

table continues on next page

SYSTEM/ORGAN /CLASS (SOC)	ADVERSE EVENT	AGENT	DOSAGE CHANGE
AT TIME OF RETREATMENT (occurring at Days 11-14 during cycle) CONTINUED			
Immune system disorders	Allergic reaction grade 1	Oxaliplatin Leucovorin	Decrease infusion rate by 50% until symptoms resolve, then resume at initial planned rate.
	Allergic reaction grade 2		Stop FOLFOX infusion. Administer H ₁ and/or H ₂ blockers and/or steroids according to local medical site policy. Restart infusion when symptoms resolve and pretreat before all subsequent doses. Treat according to local medical site policy.
	Allergic reaction grade 3 or 4		Stop the infusion. Discontinue FOLFOX. Treat according to local medical site policy.
Skin and subcutaneous tissue disorders	Extravasation	Oxaliplatin	Extravasation of oxaliplatin has been associated with necrosis. If extravasation is suspected, stop the FOLFOX infusion and restart at another site. Treat according to local medical site policy. DO NOT apply COLD.
Other Non-hematologic	Grade 3 or Grade 4	5-FU Oxaliplatin Leucovorin	Hold FOLFOX until toxicity \leq grade 1 then resume with one dose level reduction of both 5-FU and oxaliplatin
Neurological	Neurotoxicity grade 2 persisting between treatment cycles	Oxaliplatin	Continue FOLFOX with previous dose level of 5-FU and one dose level reduction of oxaliplatin for all subsequent cycles.
	Neurotoxicity grade 3 resolving to \leq grade 2 between treatment cycles		Continue FOLFOX with previous dose level of 5-FU and one dose level reduction of oxaliplatin for all subsequent cycles.
	Neurotoxicity grade 3 persisting between treatment cycles		Discontinue oxaliplatin. Continue 5-FU/leucovorin. Reassign to 5FUCMT if has not completed at least 5 cycles of FOLFOX.
	Neurotoxicity grade 4		Discontinue oxaliplatin. Continue 5FU/leucovorin. Reassign to 5FUCMT if has not completed at least 5 cycles of FOLFOX.
Cardiovascular	Cardiac ischemia or infarction grade 3 or 4		Discontinue all study therapy.
	Cerebrovascular ischemia grade 3 or 4		Discontinue all study therapy.

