3.1.4 Human Toxicology

The most common adverse reactions associated with the combination oxaliplatin/5-FU/LV were peripheral sensory neuropathies, fatigue, myelosuppression, GI toxicity and increased transaminases.

The acute, reversible, primarily peripheral, sensory neuropathy associated with oxaliplatin is of early onset, and can occur within hours or one to two days of dosing. It usually resolves within 14 days, and frequently recurs with further dosing. Symptoms include sensory dysesthesia, paresthesia and hypoesthesia of the limbs, mouth, throat and larynx. Jaw spasm, abnormal tongue sensation, dysarthria, eye pain, and a feeling of chest pressure have also been observed.

Pharyngolaryngeal dysesthesia is common, with severe symptoms in 1-2% of patients shortly after drug infusion. Symptoms usually resolve within hours of onset. The feeling of difficulty in breathing or swallowing may be distressing to the patient. Cold avoidance should be exercised. Treatment is usually not needed, although antihistamines and bronchodilators have been used. To prevent recurrence, infusion time should be extended to 6 hours with subsequent treatments.

The persistent (>14 days), primarily peripheral, sensory neuropathy is usually characterized by paresthesias, dysesthesias, hypoesthesia and altered proprioception. It can interfere with daily activities (e.g. buttoning clothing, holding objects, writing) and occurs in most patients receiving oxaliplatin with 5-FU/LV. Lhermitte's sign and urinary retention are seen rarely. Persistent neuropathy can occur without prior acute neuropathy event. Symptoms may improve in some patients upon discontinuation of oxaliplatin. Calcium gluconate 1 g and magnesium sulphate 1 g infusions pre ± post-oxaliplatin did not appear to be effective neuroprotective agents in a randomized study.

Anaphylaxis has been reported, including severe events in 2-3% of patients, and can occur during any cycle. Patients should not be re-challenged.

Pneumonitis has been reported rarely, and presents with cough, dyspnea, crackles and pulmonary infiltrates; oxaliplatin should be held pending investigation and discontinued if pneumonitis is confirmed.

Incidences of adverse events are generally similar between oxaliplatin used as single agent or with fluorouracil and leucovorin, although severe (grades 3-4) diarrhea, nausea and vomiting, and neurotoxicity are more common with combination therapy.

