Following longer IV infusions, *mucositis, hand-foot syndrome and diarrhea* occur most commonly. Diarrhea may be profuse and life-threatening following administration of leucovorin with fluorouracil. *Leukopenia* is the usual dose-limiting toxicity after IV bolus administration

Patients with dihydropyrimidine dehydrogenase deficiency (DPD) are at risk of severe lifethreatening toxicity with fluorouracil. While severe deficiency is rare, 3-4% of the population has some degree of DPD deficiency.

Excessive lacrimation occurs frequently. Transient blurring of vision, eye irritation and excessive nasal discharge have also been reported. The onset of eye symptoms may occur at any time during treatment. Fluorouracil has been demonstrated in tear fluid causing acute and chronic conjunctivitis that can lead to tear duct fibrosis.

Acute cerebellar syndrome is manifested as ataxia of the trunk or extremities, disturbance of gait and speech, coarse nystagmus and dizziness. The ataxia syndrome is related to peak plasma levels of the drug rather than to cumulative dose, and is therefore more common with bolus doses than with infusions. It usually resolves after treatment is discontinued, but may persist in some cases.

Palmar-plantar erythrodysesthesia or hand-foot syndrome has been noted with protracted and high dose continuous infusion (23-82%). The syndrome begins with dysesthesias of the palms and soles that progress to pain and tenderness. There is associated symmetrical swelling and erythema of the hand and foot. The syndrome resolves gradually over 5 to 7 days with cessation of drug infusion.

Cardiotoxicity has been reported and may be caused by coronary vasospasm, endothelial cell damage or increased thrombogenicity. It occurs in less than 10% of patients, of which up to 8% may be fatal. Cardiac effects include ECG changes, angina, arrhythmias, myocardial infarction, heart failure and are usually reported within 72 h of the first cycle of fluorouracil. Cardiotoxicity is independent of dose or underlying cardiac risk factors, but may be more common with infusions. Patients should be rechallenged only when there are no other treatment options.

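### Read literally, the FOLFOX catch-all rows resume both drugs after some lung and cardiac toxicities for which the protocol's drug sections restrict restarting, with no grade limit

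*Protocol*

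**What the plan says.** Protocol 7.1.3.1 (FOLFOX) contains four rows that matter here.

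- **Interval catch-all**, other non-hematologic events of grade 2 or higher, alopecia being the only exclusion. Agents: 5-FU and oxaliplatin. Treatment is held until at most "grade 1 then resume at next lower dose level".
- **Retreatment catch-all**, other non-hematologic events of grade 3 or 4. FOLFOX is held until grade 1 or lower, then resumed with 5-FU and oxaliplatin each one level lower.
- **Pulmonary row**: "Cough, dyspnea, hypoxia, pneumonitis or pulmonary infiltrates, grade ≥ 3". Oxaliplatin is held until interstitial lung disease is ruled out, with the further instruction "Continue 5-FU/leucovorin. Discontinue study if interstitial lung disease is confirmed".
- **Cardiovascular row**: "Cardiac ischemia or infarction grade 3 or 4", for which all study therapy stops. Cerebrovascular ischemia of grade 3 or 4 has a separate row with the same action.

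The drug-information sections cover the same toxicities without naming a grade. For pneumonitis, 3.1.4 says "oxaliplatin should be held pending investigation and discontinued if pneumonitis is confirmed". For fluorouracil cardiotoxicity, 3.3.4 lists ECG changes, angina, arrhythmias, infarction and heart failure, and says "Patients should be rechallenged only when there are no other treatment options".

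**The concern.** One protocol appears to give two instructions for the same event. A clinician using the dose-modification table finds a hold followed by a restart of both drugs. A clinician using the drug sections finds oxaliplatin stopped for confirmed pneumonitis, and fluorouracil rechallenge restricted after cardiotoxicity. The catch-all rows carry neither restriction. Their response is a lower dose level, whereas 3.3.4 describes the cardiotoxicity as unrelated to dose, so the texts also differ in rationale. What is at stake is patient safety and uniform handling of toxicity across centres.

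**Working it through.** No arithmetic applies and there is no stated figure to reproduce. The check asks, for each event and grade, which FOLFOX rows reach it on their literal scope and what the drug section says.

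| Event and grade | Named row | Retreatment catch-all (grade 3 or 4) | Interval catch-all (grade 2 or higher) | Drug section |
|---|---|---|---|---|
| Pneumonitis, grade 2 | Not reached; starts at grade 3 | Not reached | Reached: resume both drugs one level lower | 3.1.4: discontinue oxaliplatin if confirmed |
| Cardiac ischemia, grade 2 | Not reached; grade 3 or 4 only | Not reached | Reached: resume both drugs one level lower | 3.3.4: rechallenge only without other options |
| Arrhythmia or heart failure, grade 2 | None | Not reached | Reached: resume both drugs one level lower | 3.3.4, as above |
| Arrhythmia or heart failure, grade 3 or 4 | None | Reached: resume both drugs one level lower | Also within its scope | 3.3.4, as above |
| Cardiac ischemia or infarction, grade 3 or 4 | Reached: all study therapy stops | Has its own row | Has its own row | No restart instruction to reconcile |
| Pneumonitis, grade 3 or higher | Reached: hold oxaliplatin; stop on confirmed lung disease | Has its own row | Has its own row | Both stop oxaliplatin; extent of the stop differs |

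The first four lines carry the conflict. The fourth does not depend on where the boundary of grade 2 lies: the cardiovascular row names ischemia and infarction only, while 3.3.4 lists arrhythmias and heart failure as cardiotoxicity too.

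Next, does another provision settle it?

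- The general rule in 7.1.3 covers a patient with several adverse events and conflicting recommendations, and selects the lowest dose level. It does not address a single event with a stop instruction in one section and a resume instruction in another.
- The interval table covers events before Day 1 of a cycle, and the retreatment table covers events within the preceding cycle. An event on days 2 to 14 of one cycle also precedes Day 1 of the next, so the timing headings do not separate the two tables cleanly.

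On the last line of the table, 3.1.4 names oxaliplatin as the drug discontinued. The pulmonary row continues 5-FU and leucovorin during the hold, then uses a phrase that names the study and no drug. The key in 7.1.3.1 defines discontinuation as a total stop of treatment, so the row probably means all chemotherapy. That is still a wider stop than 3.1.4 describes.

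**The case against.** The strongest reply is that a row headed as other non-hematologic excludes organ systems that have rows of their own. Grade 2 lung and cardiac events are then not addressed in the table, and the drug sections fill the gap without contradiction. This reading is possible but nowhere stated: the interval row names alopecia as its only exclusion. Even on this reading, the table leaves these events without an instruction and does not point to 3.1.4 or 3.3.4.

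The second reply stands and limits the point. The schema is labelled as suggested and as a guideline. Note 5 of 7.1.1.1 lets oncologists depart from it on clinical judgment without a protocol violation, and 10.1 allows treatment to stop for unacceptable toxicity. A reader might infer that the table orders a restart; it only permits one. A reader might also infer that 3.3.4 forbids rechallenge, but it is conditional and allows it when no other option exists. Discretion lowers the weight of the conflict but does not reconcile the two texts.

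Timing is a third reply: 3.3.4 says cardiac effects usually appear within 72 hours of the first cycle, which fits the retreatment table, whose catch-all starts at grade 3. Such an event also precedes Day 1 of the next cycle, so the interval row is not excluded.

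Finally, CTCAE version 5.0 is cited but not reproduced, so which presentations count as grade 2 cannot be checked here. That stands for the grade 2 lines. It does not affect grade 3 or 4 arrhythmia or heart failure.

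**Conclusion.** The concern holds as an unreconciled conflict between 7.1.3.1 and sections 3.1.4 and 3.3.4. It rests on reading the catch-all rows by their stated scope. It is a safety wording matter that should be corrected, moderated by the schema's non-binding status. It has no bearing on sample size, power, type I error or the organ preservation endpoint.

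Its size cannot be derived. A reader might apply the figure of under 10% for cardiotoxicity in 3.3.4 to all 58 patients. That figure covers every grade and type of cardiac effect, including ischemia and infarction for which the table already stops all therapy. The 58 also include any CAPOX patients, whom this table does not govern, and the documents give no regimen split. For pneumonitis, 3.1.4 says only that it is rare.

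Two further inferences are not supported. One is that the phrase about discontinuing the study would end follow-up: the key in 7.1.3.1 ties discontinuation to treatment, 10.1 asks that follow-up continue after treatment stops, and 6.3 follows all enrolled patients until death or release by the sponsor. The other is that surgery is always available, so that the exception in 3.3.4 could never apply. Criterion 4.1.7 establishes fitness for radical surgery at entry, not after a cardiac event.

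**What to change.** Reconcile 3.1.4 and 3.3.4 with the pulmonary, cardiovascular and two catch-all rows of 7.1.3.1, so that each cardiac and pulmonary event and grade has one instruction. State explicitly whether the catch-all rows apply to these systems. As a minor wording point, state which treatment the pulmonary row stops on confirmed lung disease, since 3.1.4 names oxaliplatin only. Which instruction prevails is for the sponsor's clinicians.

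The cost is wording in an amendment or clarification memo, with no new assessments. The practical effect on dosing in this trial is probably small: SAP 2.2 records accrual closed on May 19, 2020, and planned chemotherapy lasts 6 × 14 = 84 days (FOLFOX) or 4 × 21 = 84 days (CAPOX). The correction still matters for two reasons. The sponsor can use the data behind SAP Table 18 (modifications and their reasons) and Table 42 (adverse events leading to discontinuation) to check how any such events were handled. The schema should also not be carried unreconciled into the randomized trial foreseen in Protocol 2.0.
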